## **8.2 DATA QUALITY ASSURANCE**

A risk-based approach is used for trial quality management. It is initiated by the assessment of critical data and processes for trial subject protection and reliability of the results as well as identification and assessment of associated risks. An Integrated Quality and Risk Management Plan documents the rationale and strategies for risk management during trial conduct including monitoring approaches, vendor management and other processes focusing on areas of greatest risk.

Continuous risk review and assessment may lead to adjustments in trial conduct, trial design or monitoring approaches.

A quality assurance audit/inspection of this trial may be conducted by the sponsor, sponsor's designees, or by IRB / IEC or by regulatory authorities. The quality assurance auditor will have access to all medical records, the investigator's trial-related files and correspondence, and the informed consent documentation of this clinical trial.

## **8.3 RECORDS**

CRFs for individual subjects will be provided by the sponsor. For drug accountability, refer to Section [4.1.8](#).

### **8.3.1 Source documents**

In accordance with regulatory requirements, the investigator should prepare and maintain adequate and accurate source documents and trial records for each trial subject that include all observations and other data pertinent to the investigation. Source data as well as reported data should follow the 'ALCOA principles' and be attributable, legible, contemporaneous, original, and accurate. Changes to the data should be traceable (audit trail).

Data reported on the CRF must be consistent with the source data or the discrepancies must be explained.

Before providing any copy of subjects' source documents to the sponsor, the investigator must ensure that all subject identifiers (e.g., subject's name, initials, address, phone number, and social security number) have properly been removed or redacted to ensure subject confidentiality.

If the subject is not compliant with the protocol, any corrective action (e.g. re-training) must be documented in the subject file.

For the CRF, data must be derived from source documents, for example:

- Subject identification: sex, year of birth (in accordance with local laws and regulations)

- Subject participation in the trial (substance, trial number, subject number, date subject was informed)
- Dates of subject's visits, including dispensing of trial medication
- Medical history (including trial indication and concomitant diseases, if applicable)
- Medication history
- AEs and outcome events (onset date [mandatory], and end date [if available])
- SAEs (onset date [mandatory], and end date [if available])
- Concomitant therapy (start date, changes)
- Originals or copies of laboratory results and other imaging or testing results, with proper documented medical evaluation (in validated electronic format, if available)
- ECG results (original or copies of printouts)
- Fundoscopy results
- Completion of subject's participation in the trial (end date; in case of premature discontinuation, document the reason for it, if known)
- Prior to allocation of a subject to a treatment into a clinical trial, there must be documented evidence in the source data (e.g. medical records) that the trial participant meets all inclusion criteria and does not meet any exclusion criteria. The absence of records (either medical records, verbal documented feedback of the subject or testing conducted specific for a protocol) to support inclusion/exclusion criteria does not make the subject eligible for the clinical trial.
- Volunteer Inclusion Period check documentation

### **8.3.2 Direct access to source data and documents**

The investigator /institution will allow site trial-related monitoring, audits, IRB / IEC review and regulatory inspections. Direct access must be provided to the CRF and all source documents/data, including progress notes, copies of laboratory and medical test results, which must be available at all times for review by the Clinical Research Associate, auditor and regulatory inspector (e.g. FDA). They may review all CRFs and informed consents. The accuracy of the data will be verified by direct comparison with the source documents described in Section [8.3.1](#). The sponsor will also monitor compliance with the protocol and GCP.

### **8.3.3 Storage period of records**

#### Trial site:

The trial site must retain the source and essential documents (including ISF) according to contract or the local requirements valid at the time of the end of the trial (whatever is longer).

#### Sponsor:

The sponsor must retain the essential documents according to the sponsor's SOPs.

## 8.4 EXPEDITED REPORTING OF ADVERSE EVENTS

BI is responsible to fulfil their legal and regulatory reporting obligation in accordance with regulatory requirements.

## 8.5 STATEMENT OF CONFIDENTIALITY AND SUBJECT PRIVACY

Individual subject data obtained as a result of this trial is considered confidential and disclosure to third parties is prohibited with the exceptions noted in Section [8.7](#).

Data protection and data security measures are implemented for the collection, storage and processing of patient data in accordance with the principles 6 and 12 of the WHO GCP handbook.

Personalised treatment data may be given to the subject's personal physician or to other appropriate medical personnel responsible for the subject's welfare. Data generated at the site as a result of the trial need to be available for inspection on request by the participating physicians, the sponsor's representatives, by the IRB / IEC and the regulatory authorities.

### 8.5.1 Collection, storage and future use of biological samples and corresponding data

Measures are in place to comply with the applicable rules for the collection, storage, and future use of biological samples and clinical data, in particular

- Sample and data usage has to be in accordance with the informed consent
- The BI-internal or external facilities storing biological samples from clinical trial participants are qualified for the storage of biological samples collected in clinical trials.
- An appropriate sample and data management system, incl. audit trail for clinical data and samples to identify and destroy such samples according to the informed consent form (ICF) is in place
- A fit for the purpose documentation ensures compliant usage
- A fit for purpose approach will be used for assay/equipment validation depending on the intended use of the biomarker data

Samples and/or data may be transferred to third parties and other countries as specified in the ICF.

## 8.6 TRIAL MILESTONES

The **start of the trial** is defined as the date of the enrolment of the first subject in the trial.

The **end of the trial** is defined as the 'date of the last visit of the last subject in whole trial' ('Last Subject Completed') or 'end date of the last open AE' or 'date of the last follow-up test' or 'date of an AE has been decided as sufficiently followed-up', whichever is latest.

**Early termination of the trial** is defined as the premature termination of the trial for any reason before the end of the trial as specified in this protocol.

**Temporary halt of the trial** is defined as any unplanned interruption of the trial by the sponsor with the intention to resume it.

**Suspension of the trial** is defined as an interruption of the trial based on a Health Authority request.

The EC/competent authority in each participating EU member state will be notified about the trial milestones according to the laws of each member state.

A final report of the clinical trial data will be written only after all subjects have completed the trial in all countries (EU or non-EU), so that all data can be incorporated and considered in the report.

## 10. APPENDICES

### 10.1 COVID-19 RISK ASSESSMENT AND MITIGATION STRATEGIES

The current SARS-CoV-2 pandemic can pose a challenge to integrity of the trials, protection of participants' rights, safety and wellbeing and the safety of clinical trial staff. Therefore, risk mitigation strategies will be put in place for this trial following the Central Committee on Research Involving Human Subjects (CCMO) guidance Recommendations for the conduct of clinical research at the time of restrictive measures due to the coronavirus. These mitigation strategies will be kept in place and evaluated on an ongoing basis for the duration of this trial, or until there is a consensus that the period of the SARS-CoV-2 outbreak in the Netherlands has passed. If the dynamics of the SARS-CoV-2 outbreak change in such a way that the safety of the trial participants and clinical trial staff or integrity of the data collected during this clinical trial cannot be guaranteed the trial will be halted.

#### 10.1.1 COVID-19 RISK ASSESSMENT

##### Risk for Trial Participants and Trial Staff

Healthy subjects in the current study fall in a low risk category for complications of COVID-19, the disease caused by the SARS-CoV-2 virus. To prevent SARS-CoV-2 infections among trial participants, measures and procedures based on the advice issued by the D [REDACTED] [REDACTED] ) and COVID-19 measures declared by the Dutch government will be adhered to as outlined in [REDACTED] SOP [REDACTED] procedures and measures during the COVID-19 pandemic" [[c34094272](#)]. Site trial staff in direct contact and/or within 1.5 m distance of study subjects will receive additional protection via the use of Personal Protective Equipment (PPE). All trial subjects will be screened for SARS-CoV-2 with a PCR: 1) prior to the/each admission at the clinical unit with at least one overnight stay, and; 2) in case of symptoms possibly related to COVID-19. Healthy subjects/patients will be excluded from the study when tested positive for SARS-CoV-2.

##### Protection of Trial Integrity

Adherence to the protocol and [REDACTED] SOP [[c34094272](#)] protects the integrity of the data collected during this clinical trial, as well as participants' data protection rights.

##### Impact of Investigational Drug on COVID-19 disease

Based on the mechanism of action of the investigational drug and the available information in the Investigators Brochure, there is currently no reason to believe that the investigational drug could 1) increase the susceptibility of trial participants to the SARS-CoV-2 virus, or 2) worsen or mask any COVID-19 signs, symptoms or complications.

##### COVID-19 Contingency Plan

Any subject that presents with COVID-19-related symptoms and/or has a positive SARS-CoV-2 PCR will be excluded from (further) participation in the trial and will receive follow-up medical attention per [REDACTED] SOP, see [[c34094272](#)].

## 10.1.2 COVID-19 RISK MITIGATION MEASURES

### SARS-CoV-2 Screening

Upon admission to the clinical research unit in the morning of day -1 and on day 2, a nasopharyngeal and throat swab will be taken to test for SARS-CoV-2 infection. Subjects will be required to fast for at least 1 hour prior to the nasopharyngeal and throat swab. Samples will be sent to NMDL-LCPL lab for qPCR analysis. Only subjects with a negative SARS-CoV-2 qPCR analysis prior to first dosing will be included in the study.

Subjects that test positive for a SARS-CoV-2 infection prior to the first dose will be withdrawn from the study and may be replaced. Subjects that test positive for a SARS-CoV-2 infection after the first study dose will be withdrawn from the study and may be replaced. Subjects with a SARS-CoV-2 infection will be followed-up according to SOP [c34094272].

### COVID-19 Arrival Checklist and Temperature Measurement

Trial participants are requested to come to the clinic only if they have no symptoms that could indicate a COVID-19 infection and if they have not been in contact with a COVID-19 patient according to ( ) guidelines. A standard checklist and temperature measurement are used upon arrival at the clinic.

### COVID-19 Lifestyle Restrictions

Trial participants will be required to adhere to the measures and procedures outlined in SOP [c34094272], based on the advice issued by the ( ) and COVID-19 measures declared by the Dutch government, to prevent SARS-CoV-2 infections among trial participants and clinical site staff.

## 11. DESCRIPTION OF GLOBAL AMENDMENTS

### 11.1 GLOBAL AMENDMENT 1

Date of amendment		10-Dec-2020
EudraCT number		2020-002321-28
EU number		
BI Trial number		1411-0013
BI Investigational Medicinal Product(s)		BI 474121
Title of protocol		Pharmacokinetics and pharmacodynamic effects of different single oral doses of BI 474121 in healthy male subjects
To be implemented only after approval of the IRB / IEC / Competent Authorities		
To be implemented immediately in order to eliminate hazard – IRB / IEC / Competent Authority to be notified of change with request for approval		
Can be implemented without IRB / IEC / Competent Authority approval as changes involve logistical or administrative aspects only		
Section to be changed		
 
1) 3.3. Exclusion criteria
 
2) 5.2.3 Safety laboratory parameters
 

Description of change		
 
1) Period for using highly effective methods of birth control was extended from 30 to 90 days. Consistently, the period where sperm donation is not allowed was also extended to 90 days.
 
2) GLDH and myoglobin removed
 

Rationale for change		
 
1) Request from Ethics Committee
 
2) These parameters are not available at the local lab. Safety monitoring is considered sufficient with the available parameters.
 

**11.2 GLOBAL AMENDMENT 2**

Date of amendment		14-Jan-2021
EudraCT number		2020-002321-28
EU number		
BI Trial number		1411-0013
BI Investigational Medicinal Product(s)		BI 474121
Title of protocol		Pharmacokinetics and pharmacodynamic effects of different single oral doses of BI 474121 in healthy male subjects
To be implemented only after approval of the IRB / IEC / Competent Authorities		
		
To be implemented immediately in order to eliminate hazard – IRB / IEC / Competent Authority to be notified of change with request for approval		
		
Can be implemented without IRB / IEC / Competent Authority approval as changes involve logistical or administrative aspects only		
		
Section to be changed		Table 5.2.3: 1 Routine laboratory tests in section 5.2.3  Title Page
Description of change		For the automatic differential WBC absolute instead of relative values will be provided.  Troponin T test result will be provided irrespective of whether CK is increased or not.  Title Page: Adding phone and fax number of CTL and PI
Rationale for change		Adaptations due to local lab requirements  Titel Page: Completion

[figure not shown]
[figure not shown]

## 2. LIST OF ABBREVIATIONS

See Medicine Glossary:

<http://glossary>

Term	Definition / description
AESI	Adverse event of special interest
ALT	Alanine transaminase
ANCOVA	Analysis of covariance
ANOVA	Analysis of variance
AST	Aspartate transaminase
AUC 0-tz	Area under the concentration-time curve of the analyte in plasma over the time interval from 0 to the last quantifiable data point
AUC 0-∞	Area under the concentration-time curve of the analyte in plasma over the time interval from 0 extrapolated to infinity
BLQ	Below limit of quantification
BMI	Body mass index
CI	Confidence interval
C max	Maximum measured concentration of the analyte in plasma
CSD	Company Standard Displays
CSF	Cerebrospinal fluid
cGMP	Cyclic guanosine monophosphate
cGMP base	Baseline cGMP
cGMP max	Maximum cGMP in a defined time window
cGMP min	Minimum cGMP in a defined time window
CV	Arithmetic coefficient of variation
DG	Dose group
DILI	Drug induced liver injury
F/U	Follow Up
gCV	Geometric coefficient of variation
gMean	Geometric mean
λ z	Terminal rate constant of the analyte in plasma
LLOQ	Lower limit of quantification
LLT	Lower level term
Max	Maximum

---

Term	Definition / description
MedDRA	Medical Dictionary for Regulatory Activities
Min	Minimum
N	Number non-missing observations
P10	10th percentile
P90	90th percentile
PfoS	Powder for oral solution
PDS	PD parameter analysis set
PDS-sens	PDS sensitivity analysis set
PKS	PK parameter analysis set
Q1	1st quartile
Q3	3rd quartile
R	Reference treatment
RAGe	Report Appendix Generator system
REP	Residual Effect Period
RPM	Report Planning Meeting
SD	Standard deviation
SOC	System organ class
T	Test treatment
$t_{\max}$	Time of maximum measured concentration of the analyte in plasma
TS	Treated set
ULN	Upper limit of normal
WHO-DD	World Health Organization Drug Dictionary

### **3. INTRODUCTION**

As per ICH E9 (1) the purpose of this document is to provide a more technical and detailed elaboration of the principal features of the analysis described in the protocol, and to include detailed procedures for executing the statistical analysis of the primary and secondary variables and other data.

This Trial statistical analysis plan (TSAP) assumes familiarity with the Clinical Trial Protocol (CTP), including Protocol Amendments. In particular, the TSAP is based on the planned analysis specification as written in CTP Section 7 “Statistical Methods and Determination of Sample Size”. Therefore, TSAP readers may consult the CTP for more background information on the study, e.g., on study objectives, study design and population, treatments, definition of measurements and variables, planning of sample size, randomisation.

Study data (including data entered in the RAVE EDC system and external data provided by suppliers) will be stored in a Clinical Data Repository (CDR).

Pharmacokinetic (PK) parameters will be calculated using Phoenix WinNonlin™ software (version 8.1 or higher, [REDACTED]).

The statistical analyses will be performed within the validated working environment CARE, including SAS™ (current Version 9.4, by [REDACTED]), and a number of SAS™-based tools (e.g., macros for the analyses of AE data or laboratory data; Report Appendix Generator system (RAGe) for compilation/formatting of the CTR appendices).

#### **4. CHANGES IN THE PLANNED ANALYSIS OF THE STUDY**

All analyses as planned in the CTP will be performed and are described in more detail in this TSAP. The following changes compared to the clinical trial protocol will be made:

The definition of the treated set was slightly adapted. The treated set will not be based on “randomized” subjects but will include all entered subjects who were treated with one dose of study medication.

For the second primary endpoint, a statistical model only including fixed effects was defined in the protocol. The statistical model used for the primary analysis was changed to a mixed model in order to take the repeated measures within each subject into account. Treatment group specific effects of CSF vs. plasma will be evaluated by including an interaction term of treatment group and the PK matrix to the model. The originally defined model will be computed as a sensitivity analysis.

## 5. ENDPOINTS

### 5.1 PRIMARY ENDPOINTS

This trial has two primary endpoints:

#### Section 2.1.2 of the CTP:

*The following pharmacodynamic parameters will be determined*

- *Maximum exposure-related change from baseline (calculated as ratio) of cGMP in CSF (see CTP Section 7.3.1)*

*The following pharmacokinetic parameters will be determined for BI 474121:*

- *Cmax ratio of BI 474121 in CSF compared to plasma*

A precise definition of the first primary endpoint is provided in

#### Section 7.3.1 of the CTP:

*Maximum measured exposure-related cGMP concentration in CSF (cGMPmax):*

*In subjects treated with BI 474121 this is the maximum cGMP value measured within 1 h prior and 4 h post BI 474121 Cmax in CSF.*

*For subjects treated with placebo, this is the maximum cGMP value measured within 1 h prior to and 4 h after the median BI 474121 tmax in CSF of the BI 474121 treated subjects.*

*That means, when comparing placebo and 20 mg (after Part 1), the median BI 474121 tmax in CSF of the subjects treated with 20 mg is used, and when comparing placebo and 40 mg (after Part 2), the median BI 474121 tmax in CSF of the subjects treated with 40 mg will be considered. For the final analysis, the median BI 474121 tmax in CSF for subjects treated with the highest investigated dose group will be used.*

*The tmax values of BI 474121 in CSF used to determine the time window for cGMP are based on planned times. In case one of the considered median BI 474121 tmax in CSF is not defined unequivocally the smallest planned time fulfilling the median properties will be used.*

Additionally the minimum measured exposure-related cGMP concentration in CSF (cGMPmin) will be determined, using the same time interval around Cmax of BI 474121 in CSF as used for cGMPmax.

### 5.2 SECONDARY ENDPOINTS

#### 5.2.1 Key secondary endpoints

This section is not applicable as no key secondary endpoints have been defined in the CTP.

## 5.2.2 Secondary endpoints

[figure not shown]
### Section 2.1.2 of the CTP:

- *Maximum measured concentration ( $C_{max}$ ) of BI 474121 in plasma*
- *Maximum measured concentration ( $C_{max}$ ) of BI 474121 in CSF*
- *Time from dosing to maximum measured BI 474121 concentrations in plasma and CSF ( $t_{max}$ )*
- *Maximum measured exposure-related cGMP concentration in CSF*

### Safety and tolerability endpoints

#### Section 2.2.2.2 of the CTP: *Safety and tolerability of BI 474121 will be assessed based on:*

- *Adverse events (including clinically relevant findings from the physical examination)*
- *Safety laboratory tests*
- *12-lead ECG*
- *Vital signs (blood pressure, pulse rate)*

## 6. GENERAL ANALYSIS DEFINITIONS

### 6.1 TREATMENTS

For basic study information on treatments to be administered, assignment of treatment groups and selection of doses, please refer to CTP Section 4.

This trial in healthy male subjects consists of three trial parts with the same investigational product, BI 474121, administered in different single doses (A: 40mg, B: 20mg, C: 10mg, D: 2.5mg, see [Table 6.1: 1](#)). Preliminary analyses will be performed after each trial part. Escalation to the next part will depend on the results of these analyses. If all trial parts will be conducted, a total of 24 subjects will be included to the trial.

Part 1 will be conducted as a single-blind, randomized, placebo-controlled study with 10 subjects (n=6 **treatment B**, n=4 Placebo).

Part 2 will be an open-label, non-randomized study with 6 subjects on **treatment A**.

Part 3 will be performed as an open-label, randomized study with 8 subjects in two different dose groups (n=4 in each treatment **C and D**).

For details of dosage and formulation see Table 6.1: 1:

Table 6.1: 1 Treatments and labels used in the analysis

Treatment		Short label
P	Placebo	Plc tab
D	BI 474121, 2.5mg, tablet, qd, oral	BI 2.5mg tab
C	BI 474121, 10mg, tablet, qd, oral	BI 10mg tab
B	BI 474121, 20mg, tablet, qd, oral	BI 20mg tab
A	BI 474121, 40mg, tablet, qd, oral	BI 40mg tab

#### Section 1.2.2 of the CTP:

*The Residual Effect Period (REP) of BI 474121, when measurable drug levels and/or pharmacodynamic effects are still likely to be present, is not known for this trial. Conservatively, a minimum observation period of at least 5-fold estimated  $t_{1/2}$  has been selected, and thus a REP of 7 days is assumed (...).*

For statistical analysis of AEs, vital signs and laboratory parameters, the following analysis phases are defined for each subject:

Table 6.1: 2 Analysis phases

Study analysis phase	Label	Start (inclusive)	End (exclusive)
Screening	Screening	Date of informed consent	Date/time of administration of study drug
On-treatment	Plc tab BI 40mg tab BI 20mg tab BI 10mg tab BI 2.5mg tab	Date/time of administration of study drug	Date/time of administration of study drug + 7 days (168h) or 0:00h (midnight) on the day after trial completion date, whatever occurs first
Follow-up	F/U Plc tab F/U BI 40mg tab F/U BI 20mg tab F/U BI 10mg tab F/U BI 2.5mg tab	Date/time of administration of study drug + 7 days (168h)	0:00h (midnight) on the day after trial completion date

The following AE displays will be provided in the report:

Section 15.3 and Appendix 16.1.13.1.8 (for ClinicalTrials.gov and EudraCT only) of the CTR displays:

In these displays, the on-treatment phase will be analysed (labelled with the short label of the study treatment). Screening and follow-up phases will not be included in this analysis. The following totals will be provided in addition.

For Section 15.3:

- a total over all on treatment phases with BI ("**BI Total**")

and for Section 15.3. and 16.1.13.1.8:

- a total over all on treatment phases ("**Total**")

In Section 15.4 and Appendix 16.2 (Listings) of the CTR displays, screening and follow-up periods will be included and no totals will be provided.

Tables of vital signs and laboratory values will present results by the above mentioned on-treatment phases.

For detailed information on the handling of the treatments refer to Technical TSAP ADS (analysis data set) plan and Analysis Data Reviewers guide.

In outputs for ClinicalTrials.gov and EudraCT all study parts will be combined.

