### **3.3.4 Withdrawal of subjects from treatment or assessments**

Subjects may discontinue trial treatment or withdraw consent to trial participation as a whole ('withdrawal of consent') with very different implications; please see Sections [3.3.4.1](#) and [3.3.4.2](#) below.

If a subject is removed from or withdraws from the trial prior to the administration of trial medication, the data of this subject will not be entered in the case report form (CRF) and will not be reported in the clinical trial report (CTR). If a subject is removed from or withdraws from the trial after the administration of trial medication, this will be documented and the reason for discontinuation must be recorded in the CRF; in addition, the data will be included

in the CRF and will be reported in the CTR. At the time of discontinuation, a complete end of trial examination will be performed, if possible, and the information will be recorded in the CRF. If the discontinuation occurs before the end of the REP (see Section [1.2.2](#)), the discontinued subject should if possible be questioned for AEs and concomitant therapies at or after the end of the REP in order to ensure collection of AEs and concomitant therapies throughout the REP, if not contrary to any consent withdrawal of the subject.

Since the risks of drug exposure of a (pregnant) female partner of a male study participant via the seminal fluid are yet unknown, adequate contraception as outlined in Section [3.3.3](#) is a prerequisite for participation in the study.

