## 5.2.5.2 Adverse event collection and reporting

### 5.2.5.2.1 AE collection

Upon enrolment into a trial, the subject's baseline condition is assessed (for instance, by documentation of medical history/concomitant diagnoses), and relevant changes from baseline are noted subsequently.

Subjects will be required to report spontaneously any AEs as well as the time of onset, end time, and intensity of these events. In addition, each subject will be regularly assessed by the medical staff throughout the clinical trial and whenever the investigator deems necessary. As a minimum, subjects will be questioned for AEs (and concomitant therapies) at the time points indicated in the [Flow Chart](#). Assessment will be made using non-specific questions such as 'How do you feel?'. Specific questions will be asked wherever necessary in order to more precisely describe an AE.

A carefully written record of all AEs shall be kept by the investigator in charge of the trial. Records of AEs shall include data on the time of onset, end time, intensity of the event, and any treatment or action required for the event and its outcome.

The following must be collected and documented on the appropriate CRF(s) by the investigator:

- From signing the informed consent onwards until an individual subject's end of trial:
  - All AEs (serious and non-serious) and all AESIs
  - The only exception to this rule are AEs (serious and non-serious) and AESIs in Phase I trials in healthy volunteers, when subjects discontinue from the trial due to screening failures prior to administration of any trial medication. In these cases, the subjects' data must be collected at trial site but will not be entered in the CRF or trial database and will not be reported in the CTR.
- After the individual subject's end of trial:
  - The investigator does not need to actively monitor the subject for AEs but should only report any occurrence of cancer and related SAEs and related AESIs of which the investigator may become aware of by any means of communication, e.g. phone call. Those AEs should, however, not be reported in the CRF.

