### 7.3.5 Safety analyses

Safety will be analysed based on the assessments described in Section [2.2.2.2](#). All treated subjects (TS, refer to Section [7.3](#)) will be included in the safety analysis. Safety analyses will be descriptive in nature and based on BI standards. No hypothesis testing is planned.

For all analyses, the treatment actually administered (= treatment at onset) to the subject will be used (any deviations from the randomised treatment will be discussed in the minutes of the Report Planning Meeting).

Treatments will be compared in a descriptive way. Tabulations of frequencies/proportions will be used to evaluate categorical (qualitative) data, and tabulations of descriptive statistics will be used to analyse continuous (quantitative) data.

Measurements (such as vital signs, or laboratory parameters) or AEs will be assigned to treatments (see Section [4.1](#)) based on the actual treatment at the planned time of the measurement or on the recorded time of AE onset (concept of treatment emergent AEs). Therefore, measurements planned or AEs recorded prior to first intake of trial medication will be assigned to the screening period, those between first trial medication intake and end of REP (see Section [1.2.2](#)) will be assigned to the treatment period. Events occurring after the REP but prior to end of trial termination date will be assigned to 'follow-up'. These assignments including the corresponding time intervals will be defined in detail in the TSAP. Note that AEs

occurring after the last per protocol contact but entered before final database lock will be reported to Pharmacovigilance only and will not be captured in the trial database.

Additionally, further treatment intervals (analysing treatments) may be defined in the TSAP in order to provide summary statistics for time intervals, on-treatment totals, or periods without treatment effects (such as screening and follow-up intervals).

Adverse events will be coded using the Medical Dictionary for Regulatory Activities (MedDRA). Frequency, severity, and causal relationship of AEs will be tabulated by treatment, system organ class, and preferred term. SAEs, AESIs (see Section [5.2.5.1](#)), and other significant AEs (according to ICH E3) will be listed separately.

Previous and concomitant therapies will be presented per treatment group without consideration of time intervals and treatment periods.

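### The SAP's on-treatment phase can close before the 7-day residual effect period ends, so an early leaver's adverse event may fall in no analysis phase

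*SAP*

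**What the plan says.** **Length of the REP.** SAP 6.1 repeats protocol 1.2.2: "thus a REP of 7 days is assumed".

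**Assignment of AEs in the protocol.** Section 7.3.5 places in the treatment period "those between first trial medication intake and end of REP". It applies the end-of-trial limit only to the next period, follow-up, and leaves the detailed intervals to the statistical analysis plan.

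**Subjects who leave after dosing.** Protocol 3.3.4 says: "At the time of discontinuation, a complete end of trial examination will be performed", where feasible. If that is before the REP is over, the subject should, again where feasible and unless his withdrawal of consent rules it out, be "questioned for AEs and concomitant therapies at or after the end of the REP in order to ensure collection of AEs" over the whole REP.

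**Phases in the SAP.** In Table 6.1: 2 the on-treatment phase ends at administration plus "7 days (168h) or 0:00h (midnight) on the day after trial completion date, whatever occurs first". Follow-up starts at administration + 168 h and ends at that same midnight. The AE displays in CTR Section 15.3 and for the registries use the on-treatment phase only.

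**The concern.** The protocol makes a point of collecting AEs over the whole REP from a subject who leaves early, and counts every AE in that period as on-treatment. The SAP's cut at trial completion can undo this. If the completion date is that of the examination at discontinuation, the on-treatment phase closes the following midnight, and follow-up cannot take over because it has not yet started. An AE that begins in between and is learned at the REP questioning then has no phase and does not enter the on-treatment tables.

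The protocol foresees such a case. Section 10.1.2 schedules a SARS-CoV-2 swab on Day 2 and withdraws a subject who tests positive after dosing.

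At stake is completeness of the summary AE tables in very small groups. SAP Section 7 bases percentages on all subjects in the set, so a missed event lowers the numerator and leaves the denominator as it is.

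**Working it through.** The plan gives no figure to reproduce. The check applies the interval rules of Table 6.1: 2 to each possible completion day.

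**Inputs**
- Dosing at 09:00 on Day 1 (protocol Flow Chart, approximate clock time).
- REP of 168 h (SAP 6.1).
- Planned end-of-trial visit on Days 8 to 14 (Flow Chart).
- Group sizes: 4 on placebo, 6 on 20 mg, 6 on 40 mg, 4 on 10 mg, 4 on 2.5 mg (protocol Table 3.1: 1).

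**Formulas**, for completion on Day d
- Hours from dose to the midnight after completion: M = 24d − 9.
- On-treatment length: min(168, M).
- Follow-up length: M − 168. If this is negative, the phase is empty.
- REP hours in no phase: max(0, 168 − M).

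For Day 2: M = 48 − 9 = 39 h. On-treatment lasts 39 h, follow-up has length 39 − 168 = −129 h, and 168 − 39 = 129 h lie in no phase; 129/168 = 76.8%.

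| Completion day | On-treatment (h) | M − 168 (h) | REP hours in no phase | Share of REP |
|---|---|---|---|---|
| 1 | 15 | −153 | 153 | 91.1% |
| 2 | 39 | −129 | 129 | 76.8% |
| 3 | 63 | −105 | 105 | 62.5% |
| 4 | 87 | −81 | 81 | 48.2% |
| 5 | 111 | −57 | 57 | 33.9% |
| 6 | 135 | −33 | 33 | 19.6% |
| 7 | 159 | −9 | 9 | 5.4% |
| 8 | 168 | 15 | 0 | 0% |
| 14 | 168 | 159 | 0 | 0% |

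Days 9 to 13 also give 0 h. The cut therefore never acts on a subject with the planned end-of-trial visit. It acts only when completion is recorded on Days 1 to 7.

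**Effect on a table entry.** SAP 7.8.1 counts subjects, not events. One subject is 1/4 = 25 percentage points in a group of 4 and 1/6 = 16.7 points in a group of 6. Overall incidence changes by this much only if the subject had no earlier on-treatment AE. A preferred-term row changes only if that term is new for him.

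**With the on-treatment phase ended at 168 h for everyone**, the REP hours in no phase are 0 for every completion day.

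**The case against.** The strongest reply is that the gap depends on a date the documents do not fix. Nothing available says that trial completion for an early leaver is the day of the discontinuation examination. If it is the day of the REP contact, nothing is lost. The definition may be in the technical analysis-data plan to which SAP 6.1 refers, or in the removed text of protocol 1.2.2. In addition, a subject who only discontinues treatment remains in the trial (protocol 3.3.4.1) and may still have his end-of-trial visit on Days 8 to 14. The REP contact is itself conditional, so there may be no late AE to lose. All of this stands, and it makes the point conditional and small. It does not give the cut a use: where it has any effect on a known AE, it removes one that protocol 7.3.5 counts as on-treatment.

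Three stronger readings are tempting, and the documents do not support them.

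- A reader might infer from protocol 5.2.5.2.1, "Those AEs should, however, not be reported in the CRF", that AEs learned at the REP contact never reach the database. That sentence concerns cancers and related serious or special-interest events that the investigator happens to hear of after the subject's end of trial. For subjects who leave after dosing, protocol 3.3.4 says that their data go into the CRF and the trial report. Protocol 7.3.5 keeps out of the database only AEs that occur after the last contact under the protocol, and the REP questioning is reasonably such a contact.
- A reader might infer that AE rates are biased more in groups with more discontinuations. The documents give no discontinuation rates, so this has no basis.
- A reader might infer that the SAP made an undeclared change, since its Section 4 does not list the cut. Protocol 7.3.5 leaves the interval detail to the SAP, so the table can be read as elaboration. The mismatch with the stated rule remains, but it need not be a breach.

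Finally, the event need not vanish from the report. Protocol 7.3.1 has all individual data listed, and SAP 7.8 reports dropouts' safety data as far as available. The exposure is in the summary tables.

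**Conclusion.** The point holds as a conditional gap. For a subject who leaves after dosing and whose completion is recorded before Day 8, part of the REP belongs to no analysis phase: from 9 h (Day 7) to 153 h (Day 1), and 129 h, or 77%, for Day 2. An AE that starts in that stretch and is learned at the REP questioning would be absent from the CTR 15.3 and registry tables.

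This rests on three assumptions: completion is dated before the REP contact, the contact takes place, and the AE is new for that subject in the table concerned. The expected effect is small, since it concerns early leavers only, among at most 24 subjects in an exploratory trial with descriptive safety analysis. When it does occur, one subject is 25 or 17 percentage points of a group. It is a minor correction worth making, and no evidence of biased safety results.

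**What to change.** In SAP Table 6.1: 2, end the on-treatment phase at administration + 168 h for every subject by deleting the alternative end at midnight after the trial completion date. A subject who completes before Day 8 then simply has no follow-up phase. Equivalently, keep the table and state that an early leaver's trial completion date is the later of his end-of-trial examination and the REP contact. The deletion has the advantage that it does not depend on how the date is derived.

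The cost is one line in the SAP. No data collection is added, because protocol 3.3.4 already asks for the contact. Results for subjects with the planned end-of-trial visit do not change. No denominator changes either, since the AE tables count subjects and not time at risk.
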